10.3.5 Other safety information of interest

We will also collect information on the following situations, whether they are associated with an AE or not:

• Abuse or misuse

Any occurrences of these should be reported in the same manner as SAEs (Section 10.4).

10.4 Reporting of SAEs to the Pharmacovigilance Department, CDD

All SAEs, regardless of causality, must be reported to the Pharmacovigilance Department in an expedited manner.

SAEs should be documented on an SAE report form, using the completion guidelines provided.

The SAE report form should be e-mailed to Pharmacovigilance Department within 24 hours of site staff becoming aware of the SAE.

Each episode of an SAE must be recorded on a separate SAE report form. The NCI CTCAE Version 4.02 must be used to grade each SAE, and the worst grade recorded. If new or amended

Version 4.02 must be used to grade each SAE, and the worst grade recorded. If new or amended information on a previously reported SAE becomes available, the Investigator should report this to the Pharmacovigilance department on a new SAE report form.

If the SAE has not been reported within the specified timeframes, a reason for lateness must be added on the form when sending the SAE report form to the Pharmacovigilance department.

Should the Investigator become aware of any drug-related SAEs after the patient goes 'off study', these must also be reported to the Pharmacovigilance department within the specified timelines above.

10.4.1 Events exempt from being reported as SAEs to the Pharmacovigilance department

Events specified in this section do not require reporting as SAEs in this trial, unless hospitalisation is prolonged for any reason and then an SAE form must be completed. The events must still be recorded in the appropriate section of the eCRF.

Elective admissions – Elective admissions to hospital for procedures which were planned prior to entering the trial are not SAEs. Hospitalisation for administration of the IMP according to the trial protocol is also exempt from being reported as an SAE, unless the patient experiences an event during the admission which would normally qualify as an SAE.

Death due to disease progression – Cases of death due to disease progression do not require SAE reporting, unless considered related to the IMP.

10.5 Recording of adverse events and serious adverse events in eCRFs

All AEs, including SAEs, must be recorded in the eCRF for eligible patients. All concomitant medications, including herbal medications and supplements must be recorded. Any therapy used to treat the event must be recorded. The eCRF will be reconciled with the safety database during and at the end of the trial. Therefore, the sites should ensure the data entered on the SAE report form and the data entered into the eCRF are consistent. The CDD Medical Advisor and the Investigator(s) will regularly review the safety data from both the safety and the clinical database.

10.6 Urgent safety measures

The Sponsor or Investigator may take appropriate urgent safety measures (USMs) in order to protect the patient of a clinical trial against any immediate hazard to their health or safety. This includes procedures taken to protect patients from pandemics or infections that pose serious risk to human health.

USMs may be taken without prior authorisation from the competent authority.

The Medicines and Healthcare products Regulatory Agency (MHRA) and the Research Ethics Committee (REC) must be notified within three days of such measures being taken.

Should the site initiate a USM, the Investigator must inform the Sponsor immediately either by:

The notification must include:

- the date of the USM;
- who took the decision; and
- why action was taken.

The Sponsor will then notify the MHRA and the REC within three calendar days of USM initiation.

10.7 Pregnancy

Female patients who become pregnant from the time of informed consent being signed to off-study, must be withdrawn from study treatment immediately.

The Investigator must make every effort to try and ensure that a clinical trial patient or a partner of a clinical trial patient does not become pregnant during the trial or for six months afterwards. This should be done as part of the consent process by explaining clearly to the patient (and parent/legal guardian, if appropriate) the potential dangers of becoming pregnant and also providing each patient (and parent/legal guardian, if appropriate) with information about appropriate medically approved contraception. Two forms of medically approved contraception should be used, such as:

- Oral contraceptives and condom; (oral, injected or implanted hormonal contraceptives should be used for four weeks before the patient joins the study)
- intra-uterine device (IUD) and condom;
- diaphragms with spermicidal gel and condom.

Contraception should be effective before the patient is enrolled on the trial, throughout the trial and for six months after completing the trial.

Alternatively the patient may agree to sexual abstinence, effective from the first administration of *IMP*, throughout the trial and for *six* months afterwards. Abstinence is only considered to be an acceptable method of contraception when this is in line with the preferred and usual lifestyle of the subject. Periodic abstinence (e.g., calendar, ovulation, symptothermal, post-ovulation methods) and withdrawal are not acceptable methods of contraception.

It should be explained to a male patient (and parent/legal guardian, if appropriate) that if his partner is pregnant or breast-feeding when he is enrolled on the trial, the patient should use barrier method contraception (condom plus spermicidal gel) to prevent the unborn baby or the baby being exposed to AZD3965.

However, if a patient or a partner of a patient does become pregnant, the reporting procedures below must be followed.

Any pregnancy occurring in a patient or a patient's partner during treatment with an IMP or occurring within six months of last IMP administration must be reported to the Pharmacovigilance Department within 24 hours of the site staff becoming aware of it using a Pregnancy Report Form (provided in the ITF). It is the Investigator's responsibility to obtain consent for follow-up from the patient or patient's partner. In addition, the Investigator must be made aware of the need to obtain contact details for the patient's partner's General Practitioner. The Pharmacovigilance Department will follow-up all pregnancies for the pregnancy outcome via the Investigator, using a Pregnancy Report Form.

The Investigator must ensure that all patients are aware at the start of a clinical trial of the importance of reporting all pregnancies (in themselves and their partners) that occur whilst being treated with the IMP and occurring up to six months after the last IMP administration. The Investigator should offer counselling to the patient and/or the partner, and discuss the risks of continuing with the pregnancy and the possible effects on the foetus. Monitoring of the patient or partner should continue until the conclusion of the pregnancy, if the patient or patient's partner has consented to this. Monitoring of the baby should continue until 12 months after birth, if the patient or patient's partner has consented to this.

11 ASSESSMENT OF EFFICACY

11.1 Measurement of disease

Disease must be measured according to the RECIST criteria v1.1 given in Appendix 2A or to the International Working Group (IWG) criteria for lymphoma (Cheson, Pfistner *et al*, 2014) in Appendix 2B.

11.2 Timing and type of tumour assessments

A thorough clinical and radiological evaluation of malignancy, as judged appropriate by the Investigator, and in line with the protocol, must be performed before starting the investigational medicinal product (IMP). The same methods that detect evaluable lesions at baseline must be used to follow these lesions throughout the trial. To ensure compatibility, the radiological assessments used to assess response must be performed using identical techniques. Imaging based evaluation is preferred to evaluation by clinical examination when both methods have been used to assess the anti-tumour effect of a treatment.

All radiological assessments must be performed within four weeks before starting treatment. The interval between the last anti-cancer therapy and these measurements must be at least four weeks (28 days). All clinical measurements to assess response must be done within **one** week before the patient starting treatment.

All complete (CR) and partial responses (PR) must be confirmed by two consecutive observations not less than four weeks apart.

Copies of the scans must be available for external independent review if requested by the CDD.

11.2.1 Baseline evaluations

These must include radiological measurements and as indicated chest computerised tomography (CT) scan, abdominal CT scan, magnetic resonance imaging (MRI), [¹⁸F]FDG-PET scan, bone scan and/or clinical measurements as appropriate. All areas of disease present must be documented (even if specific lesions are not going to be followed for response) and the measurements of all measurable lesions must be recorded clearly on the scan reports. Any non-measurable lesions must be stated as being present. For clinical measurements, documentation by colour photography including a ruler to estimate the size of the lesion is strongly recommended, as this aids external independent review of responses (see Appendix 2A and 2B).

If a lesion is FDG avid it can be considered to contain tumour and be measured. Any mass, of any size that is FDG negative by PET, cannot be considered to be disease. A positive scan is defined as focal or diffuse FDG uptake above background in a location incompatible with normal anatomy or physiology, without a specific standardized uptake value cut-off. Other causes of false-positive scans should be ruled out. Exceptions include mild and diffusely increased FDG uptake at the site of moderate or large-sized masses with an intensity that is lower than or equal to the mediastinal blood pool, hepatic or splenic nodules 1.5 cm with FDG uptake lower than the surrounding liver/spleen uptake and diffusely increased bone marrow uptake within weeks after treatment. Specific criteria for lung nodules based on lesion size have been developed. (Cheson, Pfistner *et al*, 2014).

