- If the positive FDG-PET at follow-up is not confirmed as a new site of disease on CT, additional follow-up CT scans are needed to determine if there is truly progression occurring at that site (if so, the date of PD will be the date of the initial abnormal FDG-PET scan). A 'positive' FDG-PET scan lesion means one which is FDG avid with an uptake greater than twice that of the surrounding tissue on the attenuation corrected image.
- If the positive FDG-PET at follow-up corresponds to a pre-existing site of disease on CT that is not progressing on the basis of the anatomic images, this is not PD.

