17.3 APPENDIX 2B: MEASUREMENT OF DISEASE IN LYMPHOMA

Below is an excerpt of text from Cheson, Fisher et al; JCO 2014, 32; 3059-3067

Response and Site	PET-CT–Based Response	CT-Based Response
Complete	Complete metabolic response	Complete radiologic response (all of the following)
Lymph nodes and extralymphatic sites	Score 1, 2, or 3 [*] with or without a residual mass on 5PS [†]	Target nodes/nodal masses must regress to ≤ 1.5 cm in LDi
	It is recognized that in Waldeyer's ring or extranodal sites with high physiologic uptake or with activation within spleen or marrow (e.g., with chemotherapy or myeloid colony-stimulating factors), uptake may be greater than normal mediastinum and/or liver. In this circumstance, complete metabolic response may be inferred if uptake at sites of initial involvement is no greater than surrounding normal tissue even if the tissue has high physiologic uptake	No extralymphatic sites of disease
Nonmeasured lesion	Not applicable	Absent
Organ enlargement	Not applicable	Regress to normal
New lesions	None	None
Bone marrow	No evidence of FDG-avid disease in marrow	Normal by morphology; if indeterminate, IHC negative
Partial	Partial metabolic response	Partial remission (all of the following)
Lymph nodes and extralymphatic sites	Score 4 or 5† with reduced uptake compared with baseline and residual mass(es) of any size	≥ 50% decrease in SPD of up to 6 target measurable nodes and extranodal sites
	At interim, these findings suggest responding disease	When a lesion is too small to measure on CT, assign 5 mm × 5 mm as the default value
	At end of treatment, these findings indicate residual disease	When no longer visible, 0 × 0 mm
		For a node > 5 mm × 5 mm, but smaller than normal, use actual measurement for calculation
Nonmeasured lesions	Not applicable	Absent/normal, regressed, but no increase
Organ enlargement	Not applicable	Spleen must have regressed by > 50% in length beyond normal
New lesions	None	None

Response and Site	PET-CT–Based Response	CT-Based Response
Bone marrow	Residual uptake higher than uptake in normal marrow but reduced compared with baseline (diffuse uptake compatible with reactive changes from chemotherapy allowed). If there are persistent focal changes in the marrow in the context of a nodal response, consideration should be given to further evaluation with MRI or biopsy or an interval scan	Not applicable
No response or stable disease	No metabolic response	Stable disease

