^{a*} A score of 3 in many patients indicates a good prognosis with standard treatment, especially if at the time of an interim scan. However, in trials involving PET where de-escalation is investigated, it may be preferable to consider a score of 3 as inadequate response (to avoid under treatment). Measured dominant lesions: Up to six of the largest dominant nodes, nodal masses, and extranodal lesions selected to be clearly measurable in two diameters. Nodes should preferably be from disparate regions of the body and should include, where applicable, mediastinal and retroperitoneal areas. Non-nodal lesions include those in solid organs (e.g., liver, spleen, kidneys, lungs), GI involvement, cutaneous lesions, or those noted on palpation. Nonmeasured lesions: Any disease not selected as measured, dominant disease and truly assessable disease should be considered not measured. These sites include any nodes, nodal masses, and extranodal sites not selected as dominant or measurable or that do not meet the requirements for measurability but are still considered abnormal, as well as truly assessable disease, which is any site of suspected disease that would be difficult to follow quantitatively with measurement, including pleural effusions, ascites, bone lesions, leptomeningeal disease, abdominal masses, and other lesions that cannot be confirmed and followed by imaging. In Waldeyer's ring or in extranodal sites (e.g., GI tract, liver, bone marrow), FDG uptake may be greater than in the mediastinum with complete metabolic response, but should be no higher than surrounding normal physiologic uptake (e.g., with marrow activation as a result of chemotherapy or myeloid growth factors).

 $\underline{a+}$ PET 5PS: 1, no uptake above background; 2, uptake \leq mediastinum; 3, uptake > mediastinum but \leq liver; 4, uptake moderately > liver; 5, uptake markedly higher than liver and/or new lesions; X, new areas of uptake unlikely to be related to lymphoma.

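### Section 11.2.1 accepts as tumour a lesion whose FDG uptake Appendix 2B already grades as a complete metabolic response, so a patient can be recorded as a CR without any change

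*Protocol*

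**What the plan says.** Section 11.2.1 (Baseline evaluations) states: "If a lesion is FDG avid it can be considered to contain tumour and be measured". It then defines positivity: "A positive scan is defined as focal or diffuse FDG uptake above background in a location incompatible with normal anatomy or physiology". No standardised uptake cut-off is set. Two of its exceptions bear on this point. One covers moderate or large masses with mild, diffuse uptake "with an intensity that is lower than or equal to the mediastinal blood pool". The other covers hepatic or splenic nodules with "FDG uptake lower than the surrounding liver/spleen uptake".

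Appendix 2B (section 17.3) grades response in lymphoma, with one column for PET-CT and one for CT. In the PET-CT column, scores 1, 2 and 3 are a complete metabolic response "with or without a residual mass on 5PS". The scale describes the middle score as "3, uptake > mediastinum but" not above liver. The rows for partial and for no metabolic response both begin at score 4.

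Appendix 2A (section 17.2), in its RECIST text on new lesions, has a further rule: a positive lesion is one that is "FDG avid with an uptake greater than twice that of the surrounding tissue".

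Section 11.1 allows disease to be measured by RECIST 1.1 or by the lymphoma criteria. Sections 11.2 and 11.3 require CR and PR to be confirmed at least four weeks later.

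**The concern.** The rule that admits a lesion as disease and the rule that declares it gone use different thresholds, and the ranges overlap. A lesion in the overlap counts as tumour at entry and already meets the complete-response definition on the same scan. If it stays as it was, the PET-CT column has no stable category to put it in.

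Anti-tumour activity is the secondary objective of Part 2, which has at most 20 evaluable patients and no control group. Complete responses will be few, so one that reflects only the choice of threshold would be conspicuous in the report and would be read as drug effect.

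**Working it through.** No figure in the plan has to be reproduced. The check is to follow one lesion through the text: a nodal mass with uptake above mediastinum and not above liver, longer than 1.5 cm, and identical at every scan.

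| Rule | Grading of this lesion |
|---|---|
| Section 11.2.1 | Positive; may be measured as tumour. The mass exception stops at mediastinal blood pool, and the liver/spleen exception does not apply to a node. |
| Appendix 2B, PET-CT column, complete | Met: score 3, residual mass allowed, no comparison with baseline. |
| Appendix 2B, PET-CT column, partial | Not available: needs score 4 or 5 and reduced uptake. |
| Appendix 2B, PET-CT column, no response | Not available: needs score 4 or 5. |
| Appendix 2B, PET-CT column, progression | Not met: needs score 4 or 5 with increased uptake, or new avid foci. |
| Appendix 2B, CT column | Stable: the decrease is 0%, below the 50% needed for partial remission, and the node has not regressed to 1.5 cm. |

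**Confirmation.** Section 11.2.2 schedules assessments every 2 cycles, so every 2 × 28 = 56 days, or 8 weeks, in Cycles 1 to 12. The second unchanged scan comes 8 weeks after the first, which exceeds the four-week minimum. The confirmation rule is satisfied by the ordinary schedule.

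**From lesion to patient.** A patient-level complete metabolic response also needs every lesion at score 3 or below, no new lesions and no FDG-avid marrow disease. The patients at issue are those who meet these conditions at baseline and stay that way.

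**Size.** One patient among n evaluable shifts the CR proportion by 1/n. With n = 20, 1/20 = 0.05, or 5 percentage points. With k such patients the shift is 5k points. The documents give no basis for k.

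**Which summary moves.** The CR proportion moves, and so does CR plus PR. The endpoint in sections 1.2.2 and 3.1.2 lists SD, PR and CR together. A count of SD or better would not move, because the alternative grading is SD.

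**The case against.** The strongest reply is that the two texts do different jobs. Section 11.2.1 identifies disease at entry and assigns no response category; Appendix 2B grades response and never defines a positive scan. That is correct, but it does not remove the problem, which arises because the two are applied in sequence to the same lesion.

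Section 11.3 speaks of confirmed changes in tumour measurements, and an unchanged lesion shows none. The wording leans against a CR here, but it sets no minimum change and does not override the appendix. Section 8.1.3 also limits PET/CT to patients with PET-avid disease, as applicable, and Part 2 requires measurable disease. Both make the case less common without excluding it. Expert review under section 11.3 is optional and would work from the same text. The appendix's caution about score 3 is offered for de-escalation trials, and the protocol does not adopt it.

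Some stronger readings are tempting and are not supported:

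- A reader might infer that every patient whose best scan is score 3 flips between CR and not-CR. A fall from score 4 or 5 to score 3 is a complete metabolic response under Appendix 2B, and nothing in 11.2.1 reverses it.
- A reader might count three incompatible definitions. The Appendix 2A cut belongs to the RECIST new-lesion algorithm for solid tumours, and the conflict does not depend on it.
- A reader might take the marrow exception in 11.2.1, which mentions uptake in the weeks after treatment, as proof that the section governs on-study scans. In relapsed or refractory patients it can equally mean prior therapy.
- The reference list gives the 2007 lymphoma criteria while the text and Appendix 2B cite 2014. This is a clerical slip.

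**Conclusion.** The point holds in a limited form. As written, the protocol permits a confirmed CR in a patient with no change, provided that all lesions score 3 or below at baseline, at least one is accepted as tumour under 11.2.1, there are no new lesions or avid marrow disease, and the PET-CT column is used. Hepatic or splenic nodules below surrounding organ uptake fall outside the conflict. The CT column would give stable disease for an unchanged enlarged node, and the protocol leaves open which column decides.

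The effect is 5 points on the CR proportion per such patient if 20 are evaluable. Their number cannot be derived from the documents, so no total effect can be claimed. The endpoint is secondary, is presented in listings (section 14.5) and carries no formal test, so what is at risk is the reported response. It is worth correcting because a false CR is possible under the plan as written and wording can prevent it.

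**What to change.** - In section 11.2.1, replace the positivity text for lymphoma with the 5-point scale of Appendix 2B, and use that scale at baseline and at follow-up.
- State in section 11.3 or Appendix 2B that a complete metabolic response requires a baseline score of 4 or 5, and that lesions at score 3 or below at baseline are assessed by the CT column. This also settles which column prevails for those lesions. Say how the two assessments combine in a patient who has lesions of both kinds.
- State that the Appendix 2A rule of twice the surrounding tissue applies only to RECIST assessment.
- Correct the lymphoma entry in the reference list.

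The cost is mainly wording. Baseline 5-point scores must be recorded from existing scans, and a few patients will be assessed by CT only.

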11.2.2 Evaluations during and at Off-study visit

Tumour assessments must be repeated every 2 cycles/8 weeks (Cycles 1-12) and every 3 cycles/ 12 weeks (Cycle 13 onwards) or more frequently, when clinically indicated. All lesions measured at baseline must be measured at every subsequent disease assessment and recorded clearly on the scan reports. All non-measurable lesions noted at baseline must be noted on the scan report as present or absent.

All patients, who are removed from the trial for reasons other than progressive disease, must be re-evaluated at the time of treatment discontinuation, unless a tumour assessment was performed within the previous four weeks.

It is the responsibility of the Principal Investigator to ensure that the radiologists are aware of the requirement to follow-up and measure every target lesion mentioned at baseline and comment on the non-target lesions in accordance with RECIST criteria or the IWG criteria for lymphoma (Appendix 2A and 2B).

